9.3 Variables

Primary Variable

To assess the non-adherence of hospital physicians to the approved European PIs of HES 130 products (see Annex 1a/1b), the primary variable will be the number and proportion of patients whose treatment during the hospital stay did not adhere to the approved European PIs regarding indication, contraindications and dosage (posology).

No specifications regarding diagnostic methods, medication or therapeutic procedures for the centres are pre-defined.

Variables to be Documented in the eCRF

A) Basic Information

An investigator or delegated trained study staff member is allowed to enter the following data into the eCRF:

- Hospital information [name, address, date (Day, Month, Year) of initial hospital accreditation, type of hospital (teaching/non-teaching, rural/urban, governmental/private)]
- Pseudonymised unique patient identifier
- Patient's hospital admission date (calendar week, year)
- Patient's discharge date (calendar week, year)
- Patient's demographics
 - Age (< 18 years or ≥ 18 years)
 - Weight

- Prehospital Field

- Crystalloids used before admission to the study hospital? (yes/no)
- HES 130 administered before admission to the study hospital? (yes/no)

If yes,

- Place/institution (ambulance vehicle, other)
- Trade name of any prescribed HES product
- HES 130 posology (dosage)

Note: Infusion of > 30 mL/kg for 24 hours of HES 130 (6 %) and > 18 mL/kg of HES 130 (10 %) for 24 hours is considered as off-label use.

Infusion of HES 130 for > 24 hours is considered as off-label use.

- HES infusion (first to last bag/bottle)
 - Start of infusion (Day, Month, Year/Time hh:mm) of first bag/bottle
 - End of infusion (Day, Month, Year/Time hh:mm) of last bag/bottle
 - Total amount infused (from first to last bag/bottle) before admission to the study hospital (mL)

[figure not shown]
B) Prescriptions at Hospital

Documentation of the variables stipulated in I. to III. (see below) starts with the first prescription. It will be considered as a new (subsequent) prescription if a change of the following occurred

- Indication at start time of HES 130 infusion OR
- Trade name OR
- Prescribing physician OR
- Main medical procedure at start time of HES 130 infusion

The variables to be documented within the first or subsequent prescriptions are depicted in Figure 1 below.

Figure 1 Documentation Flow for Prescriptions

I. Indication for First HES 130 Infusion Within a Prescription

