A specialised investigator (e.g. anaesthesiologist, emergency care physician) has to assess the case, and enter the data in the eCRF regarding indication. The specialised investigator must have been trained regarding the correct use of HES 130 by using the training material of the controlled access programme. For independent assessment this specialised investigator must not have had prescribed HES 130 for the treatment of the respective patient.

- The indication “Treatment of hypovolaemia due to acute blood loss when crystalloids alone are not considered sufficient” at the start time of first HES 130 infusion within a prescription applies? (yes/no/not possible to conclude due to retrospective design)

Note 1: Acute blood loss can be usual and/or abnormal and/or unexpected bleeding

Note 2: If the case is assessed as “not possible to conclude due to retrospective design” by the investigator, it is aimed to find a conclusion between the investigator and prescriber. If no final conclusion is reached, the assessment of the indication remains as “not possible to conclude due to retrospective design” and will not be classified as off-label use.

Note 3: In case HES was applied although the indication was not fulfilled at the start time of HES infusion within a prescription, this is judged as off-label use

If no, reason for HES 130 infusion [plain diagnosis text will be coded according to latest version of Medical Dictionary for Regulatory Activities (MedDRA)] has to be justified

If “not possible to conclude due to retrospective design”, has the prescriber been consulted by the investigator? (yes/no)

II. Contraindications Present at Start Time of HES Infusion Within a Prescription

A specialised investigator (e.g. anaesthesiologist, emergency care physician) has to assess the case, and enter the data in the eCRF regarding contraindications. The specialised investigator must have been trained regarding the correct use of HES 130 by using the training material of the controlled access programme. For independent assessment this specialised investigator must not have had prescribed HES 130 for the treatment of the respective patient.

Note 1: In the case that HES 130 product (see Annex 1a/1b) was applied although a contraindication was present and known at the start time of HES 130 infusion within a prescription, this is judged as off-label use.

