9.7 Data Analysis

9.7.1 Methods

Due to the exploratory character of this study only descriptive statistics will be used for the analysis of the variables listed in [Section 9.3](#). For continuous variables, mean \pm standard deviation, median and quartile (25th; 75th percentile) and numbers of non-missing and missing values will be presented. For categorical variables, frequencies and percentage will be shown for each category and for missing values.

Primary Variable

To assess the non-adherence of hospital physicians to the approved European PIs of HES 130 solutions (see Annex 1a/1b), the primary variable will be the number and proportion of patients whose treatment during the hospital stay did not adhere to the approved European PIs regarding indication, contraindications and dosage (posology)**. The full analysis set will comprise all eligible patients.

The number and percentage of patients who received HES 130 and were documented as non-adherent to one or more of the specifications made in the PIs (concerning the indication, contraindications and dosage) will be evaluated for the overall patient population and will be displayed together with 95 % confidence intervals for the percentage.

For the primary analysis, missing data regarding indication and posology (dosage) will neither be defined as non-adherent nor adherent prescription; this also applies if “not possible to conclude due to retrospective design” is assessed regarding indication. If more than one HES 130 prescription is reported for the same patient, every single prescription needs to adhere to the approved European PIs for counting the patient's total HES 130 treatment as adherent. That means, if at least one prescription will be non-adherent, the patient's total HES 130 treatment will be counted as non-adherent (see also Figure 3 and Figure 4 below).

Sensitivity Analyses of the Primary Variable

In addition, sensitivity analyses of the primary variable will be conducted in which “not possible to conclude due to retrospective design” regarding indication will be evaluated as

- non-adherent prescription (sensitivity analysis 1)
- adherent prescription (sensitivity analysis 2)

** Infusion of HES 130 for > 24 hours is considered as off-label use. Infusion of > 30 ml/kg for 24 hours of HES 130 (6 %) and > 18 ml/kg of HES 130 (10 %) for 24 hours is considered as off-label use.

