9.8.1 Procedures in the Participating Hospital

Each hospital designates one principal investigator (who will be supported by the appointed CRO). The principal investigator will be responsible for:

- Obtaining local Independent Ethics Committee (IEC) approval (if required by local requirements) for the conduct of the DUS in his/her HES-accredited hospital
- Obtaining a waiver for signed written patient data protection consent if required according to HES-accredited hospital/national policy

DUS to Investigate the Routine Use of Hydroxyethyl Starch-containing Infusion Solutions

FK Study Identifier: HE06-027-CNI

- Assigning site staff and ensuring that the assigned staff is properly trained (e.g. for the study protocol and eCRFs)
- Ascertainment of data accuracy, i.e. he/she is responsible for a complete and correct recording of data in the eCRFs in the respective HES-accredited hospital (he/she should apply the four-eyes principle) to assure high quality of data. Therefore, source data verification on data entered by a specialised investigator regarding indication and contraindication (in eCRF) should be performed by trained study staff member (e.g. study nurse). Application of four-eyes principle could be documented in the eCRF. In case of unresolvable discrepancies, i.e. no conclusion could be reached between both persons regarding indication and contraindication, the final decision will be taken by the local principal investigator at the respective site
- Ensuring that only qualified study staff members conduct the following:
 - A specialised investigator (e.g. anaesthesiologist, emergency care physician; see [Section 9.3](#)) has to assess the cases, enter data, and verify the data regarding indication and contraindications in the eCRF (this also applies if changes regarding indication/ contraindications occur)
 - Investigators or delegated trained study staff members are allowed to enter data on Basic Information, posology (dosage), HES 130 trade name, hospital ward, main medical procedure, crystalloid use
- Notification to the CRO, in advance of documentation and at any time after start of documentation, if the retrospective recording is not or no longer possible or feasible (e.g. due to changes in the resource situation in the participating HES-accredited hospital).

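### Indications settled with the prescriber need not be identifiable in the data, so sensitivity analyses 1 and 2 do not reach them

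*Protocol*

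**What the plan says.** The object of measurement in Protocol Section 9.3 is the prescriber's conduct: "To assess the non-adherence of hospital physicians to the approved European PIs of HES 130 products". Section 9.3, part I, separates the assessor from the prescriber: "For independent assessment this specialised investigator must not have had prescribed HES 130 for the treatment of the respective patient".

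Note 2 in the same part deals with indications that this assessor cannot conclude from the chart. For these, "it is aimed to find a conclusion between the investigator and prescriber". The inconclusive code survives only where that fails: "If no final conclusion is reached, the assessment of the indication remains as" inconclusive. The one item on consultation, "has the prescriber been consulted by the investigator? (yes/no)", is listed under the inconclusive answer.

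In Section 9.7.1 the primary analysis leaves inconclusive indications unclassified. For missing data the rule is that "missing data regarding indication and posology (dosage) will neither be defined as non-adherent nor adherent prescription", and the same sentence extends this to the inconclusive answer. Sensitivity analysis 1 counts that answer as non-adherent and sensitivity analysis 2 counts it as adherent. Analyses 3 and 4 concern missing values for selected contraindications.

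Under Section 9.8.1 a second person checks the entries on indication and contraindications. If the two cannot agree, "the final decision will be taken by the local principal investigator at the respective site".

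**The concern.** The independence rule keeps the prescriber out of the assessment, but Note 2 brings the prescriber in for the cases where the chart cannot confirm or contradict what is said. Asking is reasonable in itself. The difficulty is that a case settled this way becomes an ordinary yes or no, and the protocol does not require any trace that it was once inconclusive.

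Sensitivity analyses 1 and 2 exist to show how much the result depends on indications that the charts cannot establish. They act only on the code that remains after consultation. Each settled case leaves their reach, and the two results move closer together although the charts say no more than before. In a study meant to show whether risk minimisation measures worked, that narrowing could be read as robustness.

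A later analysis plan could not repair this, because it cannot analyse a field that was not collected.

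**Working it through.** **The plan's own figures.** At an observed rate of 50 %, the Clopper-Pearson 95 % limits are the 0.025 quantile of Beta(x, n − x + 1) and the 0.975 quantile of Beta(x + 1, n − x). The smallest n with full width at most 0.05 is 1574 (width 0.049998). For 0.06 it is 1098 (width 0.05999). Inflating for 10 %: 1574 / 0.90 = 1748.9, so 1749; 1098 / 0.90 = 1220. All of Section 9.5 reproduces, and the point does not depend on it.

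**Inputs to the illustration.** N = 1749 is the documented target in Section 9.5. The rest are assumptions, because the protocol gives no expected share of settled cases:
- 10 % of patients are inconclusive from the chart: I = 175, leaving C = 1574.
- 20 % of those 1574 are non-adherent: X = 315.
- The 175 meet the contraindication and dosage criteria, and no posology is missing.
- Inconclusive patients are left out of the primary denominator, which fits the 10 % compensation in Section 9.5.

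The 10 % is borrowed as a round number only. In Section 9.5 it covers cases finally coded inconclusive plus missing posology; it is not a rate before consultation.

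**Formulas.** Let Y be the number settled as yes, Z the number settled as no, and R = I − Y − Z the number still inconclusive.
- Primary = (X + Z) / (C + Y + Z)
- Analysis 1 = (X + Z + R) / N
- Analysis 2 = (X + Z) / N
- Analysis 1 minus analysis 2 = R / N

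**Results** (half of 175 taken as 88):

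| Settled through consultation | R | Primary | Analysis 1 | Analysis 2 | Gap (points) |
|---|---|---|---|---|---|
| None | 175 | 315/1574 = 20.0 % | 490/1749 = 28.0 % | 315/1749 = 18.0 % | 10 |
| Half, all as yes | 87 | 315/1662 = 19.0 % | 402/1749 = 23.0 % | 315/1749 = 18.0 % | 5 |
| All, as yes | 0 | 315/1749 = 18.0 % | 18.0 % | 18.0 % | 0 |
| Half, all as no | 87 | 403/1662 = 24.2 % | 490/1749 = 28.0 % | 403/1749 = 23.0 % | 5 |

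The gap depends only on R, so it narrows whichever way the cases are settled. If both analyses treated all 175 chart-inconclusive patients as inconclusive, they would give 28.0 % and 18.0 % in every row.

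**Range.** With half settled as yes, analysis 1 falls by 2.5, 5 or 10 points for a chart-inconclusive share of 5, 10 or 20 %. With all settled as yes, it falls by 5, 10 or 20 points. At a 10 % share with half settled as yes, the primary moves from 10.0 to 9.4 %, from 20.0 to 19.0 %, or from 30.0 to 28.4 %, depending on the rate among the rest.

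**The case against.** The best defence is that consulting the prescriber is not the same as letting the prescriber assess. Part of the indication is whether crystalloids alone were thought sufficient. That is the prescriber's own judgement and may not be charted, so consultation can recover real information. The non-prescribing investigator must also agree; otherwise the case stays inconclusive. This stands, and it is why the consultation should be kept. It does not make settled cases identifiable.

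A reader might infer more than the protocol supports in five respects:
- *That the eCRF definitely carries no flag.* Neither the eCRF nor the documentation flow in Figure 1 is shown. If an inconclusive answer were saved first, the consultation item might open and the audit trail (Section 9.6.1) would hold the change. The supportable statement is that the protocol does not require this and does not name the audit trail for analysis.
- *That the error runs only one way.* Consultation can end in no, and a correct yes removes missingness rather than adding error. A lean towards lower non-adherence is likely, because the person asked is the person judged, but the document does not fix it.
- *That the principal investigator escapes the independence rule altogether.* Section 9.8.1 requires a specialised investigator, as described in Section 9.3, to handle changes to indication and contraindications as well. What is missing is narrower: no express bar on a prescribing principal investigator taking the final decision.
- *That the primary rate moves by the planned interval width of 5 points.* In the central illustration it moves by about 1 point; the 5-point change is in analysis 1.
- *That the chart-only answer should become primary.* That would discard information and reduce the evaluable number against the target of 1574. It is a debatable trade-off, and this point does not require it.

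Section 9.9 does disclose that the indication may not be determinable from charts, and says that such cases will stay unassessable. It does not mention the prescriber's part in settling them.

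**Conclusion.** The point holds as a low-cost improvement to data capture and to the sensitivity analyses. It is not an error that invalidates the primary analysis. Cases settled with the prescriber are not required to be identifiable, and they fall outside sensitivity analyses 1 and 2 as defined.

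The main effect is on the upper bound. In the central illustration analysis 1 is 5 points lower than the chart evidence alone would give, and the gap between the two analyses halves, while the primary shifts by about 1 point. These sizes rest on assumed shares and on every settled patient being otherwise adherent. Patients who fail on contraindications, dosage or another prescription count as non-adherent anyway, so the real effect of a given number of settled cases would be smaller.

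**What to change.** Keep the consultation and the primary analysis as planned, and make four changes:
1. In Section 9.3, require the investigator's chart-only answer on indication to be recorded, and left unchanged, before any contact with the prescriber. Enter the answer after consultation in a separate field.
2. Ask whether the prescriber was consulted for every case that was inconclusive from the chart, whatever the final answer.
3. In Section 9.7.1, run sensitivity analyses 1 and 2 as defined, and once more with all chart-inconclusive cases treated as inconclusive.
4. In Section 9.8.1, state that whoever takes the final decision on a discrepancy must not be that patient's prescriber. A substitute decision-maker has to be named where the principal investigator is the prescriber.

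The cost is one or two extra eCRF fields, one more pair of tabulations, a few sentences of protocol text and wider sensitivity bounds. If the sponsor classes the change as a substantial amendment, Section 10.2 requires PRAC approval before implementation. The fields must be in place before data entry starts, because the chart-only answer cannot be rebuilt reliably afterwards. The sample size does not change.

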The dates for start of data collection and end of data collection have been extrapolated based on the CMDh's request to submit the study report within 24 months of the European Commission (EC) decision of 17 Jul. 2018. These dates will depend on e.g. study protocol approval, implementation period of requested risk minimisation measures, the number of available HES-accredited hospitals, the number of HES 130-treated patients, the number of physicians, CRO selection, eCRF generation, hospital selection, contract negotiations, and physicians' availability.

7 Rationale and Background

Following the publication of investigator initiated clinical trials such as 6S (Perner et al. 2012)¹, CHEST (Myburgh et al. 2012)² and VISEP (Brunkhorst et al. 2008)³, comparing HES-containing solutions with crystalloids in critically ill patients (e.g. septic patients), the EMA imposed in 2013 risk minimisation measures such as restrictions in use of HES products as specified in the European Product Information (Summary of Product Characteristics, package leaflet).

The results of two drug utilisation studies (DUSs), assessing the non-adherence of hospital physicians to the European Product Information for HES 130-containing medicinal products revised in 2014 [regarding indication, contraindications, and posology (dosage)], have shown in 2017 that the implemented restrictions for the use were not being sufficiently adhered to (ENCePP Register)⁴. Therefore, the concerned MAHs have been requested in 2018 to implement a set of further risk minimisation measures as outcome of the finalised Article 107i procedure of Directive 2001/83/EC for HES-containing medicinal products (EMA/H/A-107i/1457) [implementing European Commission decision dated 17 Jul. 2018]. These safety measures are

- Dissemination of Direct Healthcare Professional Communication to inform about the DUSs results and the outcome of the Article 107i procedure,
- Adding a box warning not to use HES in patients with sepsis, renal impairment or in critically ill patients on top of the product information,
- Training of healthcare professionals on the appropriate HES usage,
- Implementation of a Controlled Access Programme to ensure that HES solutions are only delivered to accredited hospitals where healthcare professionals expected to prescribe/administer these medicinal products have been trained on their appropriate use.

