Note: Intracranial or cerebral haemorrhage which has been corrected and was thus absent at start time of HES 130 infusion within a prescription is not to be considered as contraindication, e.g. intracranial or cerebral haemorrhage in medical history. In addition, unknown pre-existing intracranial or cerebral haemorrhage only becoming known or intracranial or cerebral haemorrhage occurring/noticed after HES 130 infusion is also not to be considered as contraindication.

Present and known at the start time of HES 130 infusion within a prescription?
(yes/no)

- Critically ill patient [typically admitted to the intensive care unit (ICU)]

Note: Critical illness which has been corrected and was thus absent at start time of HES 130 infusion within a prescription is not to be considered as contraindication, e.g. critical illness in medical history. In addition, unknown pre-existing critical illness only becoming known or critical illness occurring/noticed after HES 130 infusion is also not to be considered as contraindication.

If the patient was under special surveillance/monitoring (e.g. in a post-operative situation), but was not critically ill, this is not to be considered as a contraindication.

Present and known at the start time of HES 130 infusion within a prescription?
(yes/no)

If yes, reason why considered critically ill:

- Sepsis (yes/no)

Note: Sepsis which has been corrected and was thus absent at start time of HES 130 infusion within a prescription is not to be considered as contraindication, e.g. sepsis in medical history. In addition, unknown pre-existing sepsis only becoming known or sepsis occurring/noticed after HES 130 infusion is also not to be considered as contraindication.

Sepsis definition is provided in Annex 2.

- Other reason why considered critically ill (yes/no)

If yes, plain diagnosis text will be coded according to latest version of MedDRA

- Hyperhydration

Note: Hyperhydration which has been corrected and was thus absent at start time of HES 130 infusion within a prescription is not to be considered as contraindication, e.g. hyperhydration in medical history. In addition, unknown pre-existing hyperhydration only becoming known or hyperhydration occurring/noticed after HES 130 infusion is also not to be considered as contraindication.

Present and known at the start time of HES 130 infusion within a prescription?
(yes/no)

- Pulmonary oedema

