Furthermore, sensitivity analyses regarding the contraindications of special interest (critically ill, sepsis, renal impairment)[#] will be done. For these, missing values will be evaluated as

- non-adherent prescription (sensitivity analysis 3)
- adherent prescription (sensitivity analysis 4)

Further Analyses

Similar to the analysis of the primary variable, non-adherence to individual specifications made in the PIs will be evaluated (i.e. HES 130 use outside indication, presence of any contraindication at the start time of HES 130 infusion, presence of contraindications at the start time of HES 130 infusion by each type of contraindication and dosage outside the specifications made in the PIs).

Additionally, the number and percentage of patients whose treatment during the hospital stay does not adhere to one or more specifications made in the approved European PIs [concerning the indication, contraindications and dosage (posology)] will also be evaluated for each country.

[figure not shown]
Furthermore, analysis of non-adherence to one or more specifications made in the approved European PIs (concerning the indication, contraindications and dosage [posology]) will also be conducted for each single HES 130 prescription as statistical unit for assessment (instead of considering the patient as statistical unit) and will be presented as secondary measure.

For this purpose, each prescription is defined as a treatment with a single or multiple HES 130 infusion(s) in a row until a change of the following occurred (see also Figure 1 above):

- Indication at start time of HES 130 infusion OR
- Trade name OR
- Prescribing physician OR
- Main medical procedure at start time of HES 130 infusion OR
- The subsequent HES 130 infusion was interrupted from the previous HES 130 infusion by a HES-free interval of ≥ 24 h (see example in Figure 3). To minimise calculation errors by the sites this definition will be applied technically (and is therefore not defined in [Section 9.3](#), Figure 1).

[figure not shown]
[#] Main focus of PRAC

Figure 3 Example A for Prescription

In case the treatment duration (including HES-free interval(s) of < 24 h) exceeded 24 h and comprised several single prescriptions as defined above, only prescriptions exceeding the 24 h period will be regarded as non-adherent (see example in Figure 4 prescriptions 3 and 4).

Figure 4 Example B for Prescription

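### Sepsis is recorded only as a reason for critical illness, although the protocol treats it as a separate contraindication of special interest

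*Protocol*

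**What the plan says.** Protocol 9.3, part II, lists the contraindications that a specialised investigator assesses for each prescription. One is "Critically ill patient [typically admitted to the intensive care unit (ICU", answered yes or no. The next line is "If yes, reason why considered critically ill". Two sub-items follow: sepsis (yes/no) and "Other reason why considered critically ill (yes/no". For the sepsis sub-item the protocol says "Sepsis definition is provided in Annex 2". It cites no Annex 2 definition for critical illness. It does say that a patient under special monitoring can be judged not critically ill: "but was not critically ill, this is not to be considered as a contraindication".

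Elsewhere sepsis stands alone. Section 7 lists among the risk minimisation measures "Adding a box warning not to use HES in patients with sepsis, renal impairment or in critically ill patients". Section 9.7.1 plans sensitivity analyses for the "contraindications of special interest (critically ill, sepsis, renal impairment"), with a footnote marking these three as the main focus of PRAC. The same section plans to report non-adherence separately for each type of contraindication.

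**The concern.** The study exists to show whether the risk minimisation measures work, and the box warning on sepsis is one of them. If the form asks about sepsis only in patients already judged critically ill, two results suffer.

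- **The by-type result for sepsis.** It can never exceed the result for critical illness, whatever the charts contain.
- **The primary variable.** A patient with known sepsis, judged not critically ill and with no other violation, carries no recorded contraindication and is not counted as non-adherent.

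The item with a definition (sepsis) sits behind one for which none is cited (critical illness). A judgement therefore decides whether the defined contraindication is asked about at all. Analysis cannot repair this, because the data are never collected.

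**Working it through.** **1. Is the nesting real?** The PDF text has lost its indentation, so the wording has to settle it. The lead-in asks for the reason why the patient is considered critically ill, and the second sub-item is another such reason. Both fix sepsis as a follow-up question. No separate sepsis field appears in the variable list.

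**2. How are the other contraindications asked?**

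| Condition in 9.3, part II | How it is asked |
|---|---|
| Burns, intracranial or cerebral haemorrhage, hyperhydration, pulmonary oedema, dehydration, severe hypernatraemia, severe hyperchloraemia, severely impaired hepatic function, congestive heart failure, severe coagulopathy | Each has its own question on presence and knowledge at the start of infusion |
| Severe hyperkalaemia | Own question, conditional on the product containing potassium |
| Renal impairment; renal replacement therapy | One shared heading, but each asked independently |
| Sepsis | Only if critical illness is answered yes |

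Sepsis is the only condition whose question depends on the answer about another clinical condition. Renal impairment and renal replacement therapy show that a shared heading does not require a gate.

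**3. Could another field recover the case?** Free-text reasons are requested only when the indication is answered no or a contraindication has been recorded. Neither applies to an otherwise adherent patient. Section 9.6.2 excludes onsite monitoring, and the four-eyes check in 9.8.1 covers data that were entered.

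**4. The plan's own precision figures.** These give a scale for the bias and are not themselves affected.

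- The exact 95 % Clopper-Pearson width at p = 0.5 is 0.050014 for n = 1573 and 0.049998 for n = 1574, so 1574 reproduces. 1574 / 0.90 = 1748.9, rounded up to 1749.
- The smallest n with a width of at most 0.06 is 1098, and 1098 / 0.90 = 1220. The fallback also reproduces.

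**5. Size of the understatement.** Let s be the share of evaluable patients with known sepsis, not marked critically ill, and with no violation of indication, dosage or any other contraindication. Then

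true proportion = recorded proportion + s.

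The documents give no value for s. The values below are assumptions. With 1574 evaluable patients:

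| Assumed s | Patients missed (1574 × s) |
|---|---|
| 0.5 % | 7.9, about 8 |
| 1 % | 15.7, about 16 |
| 2 % | 31.5, about 31 |
| 3 % | 47.2, about 47 |

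Comparing the true proportion with the interval that would be reported:

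| Recorded proportion | Reported 95 % CI | s = 1 % | s = 2 % | s = 3 % |
|---|---|---|---|---|
| 10 % (157/1574) | 8.5 % to 11.6 % | 11 %, inside | 12 %, outside | 13 %, outside |
| 30 % (472/1574) | 27.7 % to 32.3 % | 31 %, inside | 32 %, inside | 33 %, outside |

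**6. The by-type result.** It misses every known-septic patient not marked critically ill, including those who are non-adherent for another reason. Its shortfall is therefore at least s.

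**The case against.** The strongest reply is that the nesting reflects the protocol's own concept. Section 7 gives septic patients as an example of the critically ill, and 9.3 lists sepsis as a reason for critical illness. On that view a trained assessor who did not prescribe the product, and who sees current, known sepsis, will answer yes to critical illness and then tick sepsis. A second person checks the entry. The content of Annex 2 is not shown and might tell sites to do this. All of this is plausible, and it may make the gap small. But no text at hand states that every septic patient is to be marked critically ill, while section 7 and 9.7.1 list the two conditions separately.

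Two stronger readings are tempting and are not supported.

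- **A reader might infer that every such septic patient counts as adherent.** That follows only if indication, dosage and all other contraindications are also met. A septic patient given the product without hypovolaemia due to acute blood loss is already non-adherent on indication.
- **A reader might infer that sensitivity analysis 3 would turn every patient not critically ill into a non-adherent one.** That requires a sepsis field left closed by design to be treated as a missing value. Section 9.7.1 does not say so, and a statistical analysis plan would normally settle it.

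The objection on cost is fair in part: under section 10.2 a substantial amendment needs PRAC approval before implementation.

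**Conclusion.** The point holds as a data-capture defect that should be fixed. As written, the sepsis result is confined to a subset of critical illness, and known sepsis in a patient not judged critically ill goes unrecorded. The primary proportion is understated by s, always downward. The size is unknown and possibly small, because s needs several conditions to hold together; the 0.5 % to 3 % range is illustrative and has no anchor in the documents. The conclusion rests on two assumptions: that the eCRF follows the variable list in 9.3, and that Annex 2 contains no instruction to mark all septic patients as critically ill. If such an instruction exists and is followed, the loss disappears. The planned sample sizes are not affected.

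**What to change.** Reconcile section 7, section 9.3 (part II) and section 9.7.1.

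- Make sepsis its own contraindication item in 9.3: a yes/no question, for every prescription, on whether sepsis was present and known when the HES 130 infusion started. Use the Annex 2 definition already cited and keep the existing note on corrected or unknown sepsis.
- Keep the reason for critical illness as a separate follow-up under that item.
- Sensitivity analyses 3 and 4 then apply to true missing values of the sepsis item.

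This changes what is recorded and no clinical rule. If sepsis always coincides with critical illness in practice, the separate item alters no result.

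The cost is one eCRF item changed before go-live and a protocol amendment that may need PRAC alignment. Time is short: the protocol is dated 09 Sep 2019 and data collection is planned from 31 Oct 2019, 52 days later.
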